### **Blinding**

Operators and care providers will not be blinded, and the outcome assessors and data analysts will be blinded to the intervention

### **Trial intervention**

#### **Delivery room**

In the delivery room, all eligible infants with spontaneously breathing should be supported by NCPAP(pressure: 6–8cm H2O) and transferred to NICUs on NCPAP immediately

#### **Nasal continuous positive airway pressure**

The infants assigned to NCPAP will be provided by either variable flow or continuous flow devices. The starting pressure will be set at 6 cmH2 O and can be raised in steps of 1 cmH2 O up to 10 cmH2 O. If this is not enough to maintain SpO2 between 90% and 95%, FiO2 will be added up to 0.40.

#### **Non-invasive high-frequency oscillatory ventilation**

NHFOV will only be provided with piston/membrane oscillators able to provide a real oscillatory pressure with active expiratory phase (Acutronic FABIAN-III, SLE 5000, Loweinstein Med LEONI+). Infants assigned to NHFOV will be started with the following boundaries: (1) mean airway pressure (MAP) of 6 cmH2O (can be changed in steps of 1 cmH2O within the range range 6–10 cmH2O); MAP will be titrated

(within the range) according to open lung strategy, performing alveolar recruitment, similar to what is done in endotracheal high frequency oscillatory ventilation targeting a  $\text{FiO}_2 \leq 25\%$  to 30%. (2) frequency of 10Hz (can be changed in steps of 1Hz within the range 8–12Hz). (3) Inspiratory time 50% (1:1). (4) amplitude 15  $\text{cmH}_2\text{O}$  (can be changed in steps of 5  $\text{cmH}_2\text{O}$  within the range 15–30  $\text{cmH}_2\text{O}$ ). In case of hypoxaemia, MAP and  $\text{FiO}_2$  will be increased (within the above-described ranges). In case of hypercarbia, amplitude will be increased first and then frequency will be lowered (within the above-described ranges).

### **Interface**

NCPAP and NHFOV will be all administered through short, binasal prongs. Nasal prongs size will be chosen according to the nares' diameter as the best fitting ones (the largest ones that fit the nares without blanching the surrounding tissues) and following manufacturer's recommendations.

### **Surfactant treatment**

Surfactant (Curosurf; 200mg/kg) will be administered if infants have  $\text{FiO}_2 > 30\%$  to maintain the target  $\text{SpO}_2$  89%–94% by less invasive surfactant administration.

### **Caffeine treatment**

Caffeine (Caffeine Citrate Injection. Chiesi Pharmaceuticals, Parma, Italy) will be prophylactic administered. The initial loading dose is 20mg/kg, and the maintenance dose is 5mg/kg per day. Caffeine treatment will be stopped when no apneas occur or corrected GA 36 weeks was reached.

### **Other treatments or tests**

(1) Heart ultrasound to evaluate cardiac morphology, pulmonary pressures and patent ductus arteriosus (PDA), within the first 3 days of life and subsequently repeated, if needed; (2) Cerebral ultrasound within 48 hours of life and weekly thereafter, until discharge, if needed; (3) Routine measures to prevent BPD; routine fluid/nutritional policy; (4) Placement of umbilical central venous catheter and/or peripherally inserted central venous lines. Placement of arterial lines if needed, according to local policies and (5) Routine therapies according to local policies (ie, antibiotics, PDA closure drugs...).

### **Primary outcomes**

The primary outcomes will be the respiratory support failure determined by the need for IMV within 72 hours from birth. The respiratory support failure will be considered if one of the following occurs: (1) severe respiratory acidosis (defined as  $\text{PaCO}_2 > 60 \text{ mm Hg}$  with  $\text{pH} < 7.2$ ) for at least 1 hour; (2) hypoxia refractory to study intervention (defined as  $\text{SpO}_2 < 90\%$ , with  $\text{FiO}_2 = 0.4$  and maximal pressures allowed in the study arm) for at least 1 hour after the administration of surfactant; (3) severe apnoea (defined as recurrent apnoea with  $> 3$  episodes/hour associated with heart rate  $< 100/\text{min}$  or a single episode of apnoea requiring bag and mask ventilation) and (4) attending physician determined that urgent intubation is necessary.

### **Secondary outcomes**

- (1) Airleaks (pneumothorax and/or pneumomediastinum) occurred during treatment of RDS.
- (2) BPD, defined according to the NICHD definition.

- (3) Haemodynamically significant PDA, defined according to local NICU protocols.
- (4) Retinopathy of prematurity (ROP) >2nd stage.
- (5) Necrotising enterocolitis (NEC)  $\geq$ 2nd stage.
- (6) Intracranial haemorrhage (IVH)  $\geq$ 3rd grade.
- (7) In-hospital mortality.
- (8) Composite mortality/BPD
- (9) Weekly weight gain (in grams/day) for the first 4 weeks of life or until NICU discharge, whichever comes first
- (10) Duration of non-invasive respiratory assistance.
- (11) Duration of hospitalisation.
- (12) Rate of surfactant treatment.
- (13) Rate of thick secretions causing an airway obstruction.
- (14) Rate of nasal trauma

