### **Sample size calculation**

According to the results of our last multicentre study, the risk of failure while receiving NCPAP for very preterm infants with RDS was 30%, and a reduction of 20% for babies receiving NHFOV. We decide to aim a difference of 15% in the rate of the respiratory support failure. Considering an alpha error of 0.05 and a power of 90%, 170 neonates would be needed in each group.

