### **Statistical methods**

Outcomes will be analysed on an intention-to-treat basis. We will calculate a risk difference (with 95%CI) for dichotomous outcomes and mean (with 95%CI) or median (25–75th percentile, using Hodges-Lehmann) differences for continuous outcomes between the study groups. Continuous variables will be compared using

Student's t test or the Mann-Whitney rank sum test as appropriate. Categorical variables were compared using the  $\chi^2$  test. P values  $< 0.05$  were considered statistically significant.

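### Secondary outcome (9), weekly weight gain over 4 weeks, has no fixed summary across weeks and no birth-weight adjustment; one adjusted 4-week estimate would be a cheap improvement

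*Combined protocol and SAP*

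**What the plan says.** In the combined protocol and SAP, Secondary outcomes item (9) reads "Weekly weight gain (in grams/day) for the first 4 weeks of life or until NICU discharge, whichever comes first".

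Statistical methods has one rule for every continuous outcome. The effect estimate is a mean difference or "median (25–75th percentile, using Hodges-Lehmann) differences for continuous outcomes between the study groups". The test is "Student's t test or the Mann-Whitney rank sum test as appropriate". P values below 0.05 "were considered statistically significant". The analysis set is given by "Outcomes will be analysed on an intention-to-treat basis".

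The documents state no summary across weeks, repeated-measures model, baseline covariate, multiplicity rule, or handling of weeks lost to death.

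Three other sections bear on the point:
- **Inclusion criteria** admit infants from 24+0 to 28+6 weeks.
- **Randomization** is simple and 1:1, with no stratification stated, and twins share an allocation.
- **Data collection** lists weekly weight gain at follow-up. At baseline it has a general clinical item and two scores, but does not name birth weight.

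**The concern.** A t or Mann-Whitney test takes one independent value per infant. An outcome recorded weekly for four weeks can supply up to four correlated values, so the rule cannot be applied until someone decides whether to test each week, pool infant-weeks or average within infant. The plan leaves that decision open, and it could be made after the data are seen.

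The outcome is also in absolute g/day, in infants spanning almost five weeks of gestation. Part of its spread probably reflects birth size. With simple randomisation, birth weight is balanced only by chance, and an unadjusted comparison leaves that variation in the error term.

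At stake are the precision and clarity of one secondary result. No decision rule in the documents depends on it.

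**Working it through.** **1. The plan's own figure.** The only calculation in the plan concerns the binary primary outcome: "Considering an alpha error of 0.05 and a power of 90%, 170 neonates would be needed in each group", with "We decide to aim a difference of 15% in the rate of the respiratory support failure", taken here as 30% versus 15%, two-sided.

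n = [1.960·√(2·0.225·0.775) + 1.282·√(0.30·0.70 + 0.15·0.85)]² / 0.15² = 161 per group, or 174 with continuity correction. The stated 170 is within 3% of 174. Power at 170 per group is 91.5%. The figure is reproduced, but it says nothing about weight gain. It serves here only as the number of infants per group.

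**2. Inputs that must be assumed.** The documents give no SD for weight gain, no correlation between weeks (ρ) and no correlation of birth weight with gain (r). I assume equal weekly SDs, complete data, ρ from 0 to 0.7 and r from 0.1 to 0.5.

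**3. Reading A: four separate weekly tests at 0.05.** With independent weeks, the chance of at least one false positive is 1 − 0.95⁴ = 18.5%. Simulating four equally correlated normal statistics (1,000,000 draws) gives:
- ρ = 0.3: 17.4%
- ρ = 0.5: 15.6%
- ρ = 0.7: 13.0%

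**4. Reading B: infant-weeks pooled as if independent.** The true variance is 1 + 3ρ times the variance the test assumes, so the real type I error is 2·[1 − Φ(1.96/√(1 + 3ρ))]. This is 15.5% at ρ = 0.3 and 21.5% at ρ = 0.5.

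**5. Reading C: each infant's weeks averaged, then one test.** Twins aside, this is one valid test at 5%. With complete data, a repeated-measures model whose arm effects are averaged equally over weeks gives the same arm difference, so any extra precision comes from birth weight alone. Adjustment multiplies the SE by √(1 − r²) and is equivalent to 170/(1 − r²) unadjusted infants per group. The unadjusted SE is √(2/170) = 0.108 SD of the infant mean, and the difference detectable with 80% power is 2.80 × 0.108 = 0.304 SD.

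| Assumed r | SE multiplier | Equivalent n per group | Detectable difference (SD) |
|---|---|---|---|
| 0.1 | 0.995 | 172 | 0.302 |
| 0.3 | 0.954 | 187 | 0.290 |
| 0.5 | 0.866 | 227 | 0.263 |

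**6. The same in g/day, for illustration.** Assume a birth-weight SD of 200 g, a between-infant SD of 3 g/day, a weekly SD of 5 g/day, and gain rising by 0.5 to 1.5 g/day per 100 g of birth weight.
- Adjusted variance of an infant's 4-week mean: 9 + 25/4 = 15.25, so SE = √(2·15.25/170) = 0.42.
- Unadjusted: birth weight adds (200·0.005)² = 1 to (200·0.015)² = 9, so SE = √(2·16.25/170) = 0.44 to √(2·24.25/170) = 0.53.
- The upper slope implies r = √(9/24.25) = 0.61, which is beyond the range in step 5, so 0.53 is an optimistic case for adjustment.

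**The case against.** The strongest reply is that item (9) is one outcome over one window, expressed as a rate. One average per infant is a natural reading, and the planned test is then single and valid. An unadjusted comparison is also unbiased under randomisation. This stands, and it limits the point to the undefined summary and the unused birth weight.

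A reader might go further and infer that the plan commits to four P values. It does not: it never says whether weeks are tested separately, pooled or averaged, so the 13% to 18.5% is conditional on one reading.

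A reader might also set a 4-week average against a single week and claim a large gain in precision. Under the assumptions in step 6, the single-week variance is 35 to 43 against an adjusted 15.25, a ratio of 2.3 to 2.8. But those are different quantities, and the ratio depends on a low between-week correlation. At ρ = 0.7 the unadjusted ratio is only 4/(1 + 3·0.7) = 1.29. It should not be presented as the benefit of changing the plan.

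The multiplicity benefit is small too. The plan lists 14 secondary outcomes at 0.05 with no hierarchy. If all were independent nulls, one test each gives 1 − 0.95¹⁴ = 51%. Testing one of them four times gives 1 − 0.95¹⁷ = 58%.

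Finally, a careless model could be worse than the simple test. An infant random effect alone ignores twins. A single birth-weight slope assumes that early and later weeks behave alike. A mixed model also implicitly estimates gain after death. The fix has to deal with all three.

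**Conclusion.** The point holds as a modest improvement to one secondary analysis. The plan fixes no single summary across weeks for outcome (9) and leaves birth-size variation in the error term.

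Its size depends on how the rule would have been applied. Separate weekly tests would carry a 13% to 18.5% chance of at least one false positive. Averaging within infant already gives one test, and birth-weight adjustment then reduces the SE by between 0.5% and 13%. All these figures rest on assumed correlations and complete data with 170 per group. Adjustment improves precision for any material correlation; only the amount is uncertain.

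The documents do not support calling the planned analysis invalid. The primary analysis and sample size are untouched.

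**What to change.** Add to Statistical methods, for outcome (9):
- **One reported result.** Give the arm difference in weight gain averaged over weeks 1 to 4, with 95% CI. Week-specific differences are descriptive.
- **Model.** Use a regression or repeated-measures model with arm, week, arm-by-week, birth weight and birth-weight-by-week. Cluster standard errors by mother, because twins share an allocation; this also covers repeated weeks within an infant.
- **Meaning.** Describe the estimate as gain while alive and in the NICU. Show the number of infants contributing per week by arm, with deaths listed.
- **Data.** Confirm that birth weight is a case-report-form item. Gain in the first week needs a starting weight, so this should require no new measurement.

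The cost is a few sentences and slightly more programming. The downside is a missing-at-random assumption for lost weeks. It is least comfortable for deaths, hence the counts by week and arm.

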### **Randomization**

Neonates will be randomised and assigned either to NCPAP or NHFOV arms with a 1:1 ratio, when patients fulfil all inclusion criteria. Simple randomisation will be done according to a computer-generated random number table and will be posted in a

specific secured website available on 24/7. Twins will all be allocated in the same treatment group. Infants randomised to one arm cannot crossover to the other or vice-versa during the study.

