### **Data collection**

All data for trial analysis are routine clinical items that can be obtained from the clinical notes. Data will be recorded in real time (every day) on web-based case report

forms provided by OpenCDMS. The website will be tested with fictitious data before the actual enrollment

Before the intervention begins: information on eligibility; baseline clinical informations, Silverman score, Critical risk index for babies-II score.

Following study intervention: ventilator parameters, SpO2, blood gas values (PaO2, PaCO2, SpO2 and pH) before intervention and intubation.

Follow-up: failed on assigned NIV at 72 hours or 7days, surfactant treatment, duration of the study intervention (NCPAP or NHFOV), airleaks, PDA, BPD, ROP >2nd stage, NEC ≥2nd stage, IVH >2nd grade, in-hospital mortality, composite mortality/BPD, weekly weight gain (in grams/day), duration of hospitalisation, thick secretions causing an airway obstruction, nasal trauma. fictitious data before the actual enrolment.

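### Durations of non-invasive support and of hospital stay are compared as raw durations, so early failure can shorten the first and death the second, and the worse arm can look better

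*Combined protocol and SAP*

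**What the plan says.** The Secondary outcomes section lists "Duration of non-invasive respiratory assistance" as item (10) and "Duration of hospitalisation" as item (11). Neither has a start, a stop, or a rule for intubation or death. The Data collection section names a related but differently worded item, "duration of the study intervention (NCPAP or NHFOV").

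Statistical methods gives one approach for all continuous outcomes: "Student's t test or the Mann-Whitney rank sum test as appropriate", with mean differences or "median (25–75th percentile, using Hodges-Lehmann) differences for continuous outcomes between the study groups". The same section says "Outcomes will be analysed on an intention-to-treat basis", so infants who fail or die stay in the comparison.

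The primary outcome is failure, determined by "the need for IMV within 72 hours from birth". On what may follow failure, the Randomization section says only "Infants randomised to one arm cannot crossover to the other or vice-versa during the study". In-hospital mortality and the mortality/BPD composite are separate secondary outcomes and are not linked to the durations. No section provides a free-days measure, a worst rank, a competing-risk method or a survivors-only analysis.

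**The concern.** A duration is a fair yardstick only if it ends for the same reason in both arms. Time on the assigned mode can end because the infant improved, was intubated or died. The trial is designed around the expectation that intubation will be twice as common on NCPAP. If NHFOV works as hypothesised, and infants who do not fail need support for equally long in both arms, the planned test can report that NHFOV prolongs support.

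Hospital stay has a similar problem with a different cause. An infant who dies on day 2 contributes a 2-day stay, so an arm with more deaths can appear to shorten hospitalisation. In both cases a secondary result could seem to contradict the primary result, or the mortality result, purely because of how the duration is scored.

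**Working it through.** **Inputs from the protocol.** Failure on NCPAP is 30%. The target difference is 15 points (read as absolute, so 15% on NHFOV). Alpha is 0.05 (two-sided assumed), power 90%, with 170 per arm.

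**Inputs assumed.** All durations, mortality rates and times of death are assumed, because the documents give none.

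**The plan's own figure.** n = [1.96·√(2·0.225·0.775) + 1.2816·√(0.30·0.70 + 0.15·0.85)]² / 0.15² = (1.157 + 0.745)² / 0.0225 ≈ 161 per arm. With continuity correction it is 174, and 161/0.95 gives 170. Power at 170 is 91.5%. The 170 is therefore consistent with 30% vs 15%.

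**Outcome (10), support ending at failure.** Let infants who do not fail have mean duration μ in both arms, and let failures stop uniformly over 0–3 days (mean 1.5).

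- NCPAP mean = 0.70μ + 0.30·1.5; NHFOV mean = 0.85μ + 0.15·1.5; gap = 0.15(μ − 1.5).
- μ = 7: 5.35 vs 6.18 days. μ = 21: 15.15 vs 18.08. μ = 30: 21.45 vs 25.73. NCPAP, the worse arm, is shorter each time.

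The rank test can be checked by hand. If every failure ranks below every non-failure, the chance that an NCPAP infant has the shorter time is 0.30·0.85 + ½(0.30·0.15 + 0.70·0.85) = 0.255 + 0.320 = 0.575. The null standard error is √[341/(12·170·170)] = 0.0314, so z = 0.075/0.0314 = 2.39 and the chance of significance is Φ(2.39 − 1.96) ≈ 67%.

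Simulated Mann-Whitney results (lognormal durations in non-failures, log-SD 0.6):

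| Treatment of failures | NCPAP significantly shorter |
|---|---|
| Support ends at failure, success median 10–30 days | about 64–68% |
| Support ends at failure, success median 3–5 days | about 36–58% |
| Half the usual duration also counted after extubation | about 2–28% |
| Full usual duration also counted after extubation | 2% or less |

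Gamma-distributed durations (means 7 to 30 days, support ending at failure) gave 50–67%, with no significant result in the opposite direction. If all support after extubation counts, failure can lengthen the total: with a mean of 21 days in non-failures, the arm means are 21.4 (NCPAP) vs 21.2 days, or 24.5 vs 22.8 if failures need 10 further days.

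**Outcome (11).** Let survivors stay a mean of 75 days (SD 20) in both arms, deaths occur uniformly over days 0–28 (mean 14), and mortality be 15% vs 10%. The gap is 0.05·(75 − 14) = 3.05 days, shorter in the arm with more deaths. This is significant in about 17–18% of trials by t test and 12–13% by Mann-Whitney. If failure adds 14 days in survivors, these fall to about 6% and 3–4%. In a second setting (survivors 70 days, deaths at 0–21 days), equal 10% mortality and the same 14 added days reverse the direction: 67.8 days in the higher-failure arm vs 65.9.

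**After the fix.** Ranking failures worst for (10) takes wrong-direction significance to 0%, and the higher-failure arm is significantly worse in about 66–69% of trials. Ranking deaths worst for (11) takes wrong-direction significance to about 0%.

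**The case against.** The strongest reply is that the large figure for outcome (10) depends on one reading. The outcome as listed is broader than the collected item, and nothing says the clock stops for good at first intubation. The crossover bar would allow a return to the assigned mode after extubation. If that time counts, the effect is small or absent. This stands: it is why the result is given as a range and why the two sections need reconciling. It does not remove the problem, because the direction of the comparison then depends on an undefined term.

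The similar results at medians of 10, 20 and 30 days are also weak evidence of robustness. At those medians nearly all failures rank lowest, so the test largely restates 30% vs 15%. That stands too, and the lower figures at 3–5 days are included for this reason.

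A reader might infer that early failure also shortens hospital stay. The documents do not support that: only death does so directly, and failure may lengthen stay in survivors. A reader might also infer that the plan will produce misleading results. It can, but no mortality rate or duration is given, so the likelihood cannot be fixed.

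Finally, the protocol names no favourable direction for either duration, a raw duration is a fair description of resource use, and deaths are reported alongside. All true, but reporting mortality separately does not correct a between-arm test of duration.

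**Conclusion.** The concern holds in a limited form. The stated analysis makes no allowance for intubation or death, so it can credit either as a short duration.

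For outcome (10), the arm with more failures is significantly shorter in about 36–68% of simulated trials if support ends at failure, and in about 0–28% if later support counts. Only the failure rates and the 170 per arm are the protocol's. For outcome (11), the artefact needs a mortality difference: about 3 days and 12–18% of trials at an assumed 15% vs 10%, and less if failure lengthens survivors' stay.

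These are two of 14 secondary outcomes. The primary analysis and sample size are unaffected, and the priority is modest.

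**What to change.** - **Outcome (11).** Give infants who die the worst rank, tied with one another, and compare arms with the Mann-Whitney test already planned. Show survivors-only durations as description. State whether stay is followed after the exit at 36 weeks' postconceptional age given under End of the study.
- **Outcome (10).** Reconcile Secondary outcomes with Data collection by stating whether support after extubation counts. Report the raw duration as description only. Base the comparison on days alive without invasive ventilation to day 28, with death scored zero, after confirming that the daily case report form records invasive-ventilation days. If it does not, rank infants who fail or die as worst and use the same Mann-Whitney test.

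**Cost.** Some analysis-plan wording and possibly one more form item, since the Data collection list does not mention invasive-ventilation days. The measures are slightly less intuitive than raw days, and days without invasive ventilation is a different quantity from outcome (10), which is why the raw duration should still be described. Sample size does not change.
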